The stimulation through the BCR can be reduced with ibrutinib, which is an oral drug that selectively inhibits Bruton's tyrosine kinase (BTK). In clinical trials, ibrutinib demonstrated safety and high response rates in patients with high-risk disease. Ibrutinib has gained FDA approval as a treatment for CLL patients with 17p deletion and for those who had at least one prior therapy. However, single-agent ibrutinib has limitations; the drug does not eliminate all the tumor cells, and, with time, the tumor cells may become resistant. Therefore, combination of ibrutinib with other drugs could be beneficial. Here we chose fludarabine because it is a well-tolerated drug that has been used widely to treat CLL. Also, fludarabine can kill both malignant B cells and T cells that support the growth of leukemia cells. With this approach we hope to restore healthier immune system.

This study will investigate the safety and efficacy of ibrutinib combined with fludarabine. This protocol is intended for previously untreated CLL patients. Ibrutinib will be given daily until disease progression or intolerable side effects occur. Fludarabine will be given only in cycles 3 and 4.

1.0	OBJECTIVES	6
1.1	PRIMARY OBJECTIVE	6
1.2	SECONDARY OBJECTIVES.....	6
2.0	BACKGROUND AND SCIENTIFIC JUSTIFICATION.....	6
2.1	PATHOPHYSIOLOGY.....	6
2.2	EPIDEMIOLOGY AND CLINICAL COURSE OF CLL.....	7
2.3	DIAGNOSTIC AND PROGNOSTIC CATEGORIES OF CLL/SLL.....	7
2.4	INDICATIONS FOR CLL TREATMENT	8
2.5	CURRENT TREATMENT OPTIONS FOR CLL/SLL.....	9
2.5.1	Watchful Waiting	9
2.5.2	First-line Chemotherapy/Immunotherapy/Chemoimmunotherapy	9
2.5.3	Complications of Chemoimmunotherapy	10
2.5.4	Relapsed or Refractory CLL	10
2.5.5	Stem Cell Transplantation:	11
2.5.6	Targeted Tyrosine Kinase Inhibitors	11
2.5.7	Other Options	11
2.6	IBRUTINIB	12
2.6.1	Mechanism of Action, Distribution, Metabolism and Clearance ⁴⁸	12
2.6.2	Clinical Experience in CLL	12
2.7	SUMMARY OF CLINICAL SAFETY	14
2.7.1	Clinical and scientific justification for protocol design	15
3.0	STUDY DESIGN.....	16
4.0	ELIGIBILITY ASSESSMENT AND ENROLLMENT.....	17
4.1	INCLUSION CRITERIA.....	17
4.2	EXCLUSION CRITERIA	17
5.0	TREATMENT PLAN.....	18
5.1	DRUG ADMINISTRATION.....	18
5.2	THERAPY SCHEDULE:	19
5.3	PROPHYLACTIC MEDICATIONS:	19
5.4	HOLDING AND DOSE ADJUSTMENTS OF STUDY DRUG ADMINISTRATION IN THE CASE OF TREATMENT RELATED TOXICITY.....	19
5.4.1	Cytopenia:	19

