3.0 STUDY DESIGN

This is a phase II single center trial. It is a prospective, single-arm, open-label study of ibrutinib and a short-course fludarabine in previously untreated subjects with CLL or SLL. Each cycle is 28 days. Patients will initiate ibrutinib first for cycle 1 and 2, followed by the addition of short-course fludarabine for cycle 3 and 4. Ibrutinib will be given continuously until disease progression or intolerable side effects.

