5.0 TREATMENT PLAN

5.1 Drug administration

Ibrutinib is an orally administered product. Study drug ibrutinib administration will take place in the outpatient facility of the NIH clinical center or at the patient's home. The drug dose is 420 mg PO daily. There is one specific dietary restriction to avoid grapefruit juice and Seville oranges due to CYP450 3A4 inhibition. Each dose of ibrutinib is to be taken with 8 ounces (approximately 240mL) of water. The capsule should be swallowed intact and subjects should not attempt to open the capsule or dissolve them in water. Ibrutinib will be given daily until disease progression or intolerable side effects.

Fludarabine is given as an intravenous infusion on cycle 3 and 4. Fludarabine administration will take place in the Clinical Center Day hospital. At the PI's discretion, select subjects may be admitted to the inpatient unit for the first few days of fludarabine infusion. Subjects will have a peripheral line placed. Per PI discretion, a central line may be placed in select patients. Fludarabine dose is 25 mg/m²/day on days 1-5 of cycles 3 and 4. Dosing will be based on actual weight for all patients. No dose adjustment is required based on age. In the event of renal impairment, dose reduction will be as follows;

- Creatinine clearance of 30-70 mL/min/1.73m² using the CKD-EPI equation with actual body weight: Fludarabine will be dose reduced by 20%.
- Creatinine clearance of ≤ 30 mL/min/1.73m² using the CKD-EPI equation with actual body weight: Fludarabine will be held at the discretion of the PI.

5.2 Therapy schedule: All cycles will be 28 (+/- 5) days long.

- Cycle 1 and 2: ibrutinib 420mg PO daily on day 1-28
- Cycle 3 and 4: ibrutinib 420mg PO daily on day 1-28, fludarabine 25mg/m²/day on day 1-5
- Cycle 5 and subsequent cycles up to C27: ibrutinib 420mg PO daily on day 1-28

5.3 Prophylactic Medications:

- Allopurinol 300mg PO once daily (or alternative agent in case the subject cannot tolerate allopurinol) during cycle 3 and 4 on days 1-7 for all subjects
- Sulfamethoxazole/trimethoprim DS PO once daily 3 times per week (or alternative agent in case of sulfa allergy) from cycle 1 to 9 and beyond at the discretion of the PI
- Acyclovir 800 mg PO twice daily or valacyclovir 500mg PO once daily at the discretion of the PI (not mandatory)

5.4 Holding and dose adjustments of study drug administration in the case of treatment related toxicity

5.4.1 Cytopenia:

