5.5 Holding of Study Drug Administration

5.5.1 Ibrutinib and Surgical Procedures:

Consider the benefit-risk of withholding ibrutinib for at least 3 to 7 days pre and post-surgery depending upon the type of surgery and the risk of bleeding.

5.5.2 Medically Necessary Conditions to Hold Study Drugs:

- If medically necessary reasons to hold ibrutinib occur during treatment (i.e. concurrent infection, impending workups for diagnostic and/or therapeutic purposes), ibrutinib can be held based on the study team's discretion.
- If medically necessary reasons to hold fludarabine occur during treatment (i.e. concurrent infection, emergence of autoimmune cytopenia, impending workups for diagnostic and/or therapeutic purposes), fludarabine can be delayed up to 2 cycles while continuing ibrutinib until the medical reasons to hold fludarabine resolve or return to baseline. If fludarabine is delayed beyond 2 cycles, fludarabine will be omitted and the patient will continue treatment with ibrutinib only.
- Supportive medications including allopurinol, and acyclovir (if indicated) intended to start at cycle 3 will be delayed until fludarabine starts or not given if fludarabine is omitted. Weekly labs intended for cycles 3 and 4 will be delayed until fludarabine starts or not performed if fludarabine is omitted.

5.5.3 Permanent discontinuation of study drug administration in case of treatment related adverse events:

- Serious or life threatening cardiac arrhythmias (grade 3 or 4)
- Severe infection (requiring vasopressor support > 24h, or intubation)
- Any grade 4 toxicity excluding readily reversible metabolic or laboratory abnormalities or hematologic toxicities
- Progressive disease as defined in section 7.3
- Pregnancy or unwillingness to use acceptable method of contraception

Patients who will not be able to receive further study drug administration will be followed for safety and after resolution of the event will continue to be followed at regular intervals and will undergo reassessment of disease as outlined in section 6 and 7.

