6.2 On therapy evaluations (see schedule of events Appendix A)

From cycle 1 to 6 (+/- 5-day window):

Prior to each cycle, the following assessments will be completed. If the assessments have been already performed within 5 days of the study drug initiation as a part of screening or baseline evaluations, the study team can decide whether these assessments may or may not be repeated.

- Interval History
- ECOG performance status evaluation
- Physical exam
- Concomitant medication review
- CBC with differential
- Acute Care Panel (Na, K, Cl, CO₂, Creatinine, Glucose, and Urea Nitrogen)
- Mineral Panel (Phosphorus, Magnesium, Albumin, and Calcium)
- Total Protein, Uric Acid, and LDH
- Hepatic Panel (Alk Phosphatase, ALT, AST, Total Bilirubin, and Direct Bilirubin)
- Reticulocyte count
- Beta-2 microglobulin (B2M)
- Direct antiglobulin test (DAT)
- For females of childbearing potential, repeat pregnancy test
- Research blood (up to 80ml)

Additional blood draws, procedures, or imaging include (+/- 5-day window, except for CT scan and bone marrow biopsy):

Cycle 3&4

- Prior to Cycle 3 (within day -14 to 0): Lymphocyte phenotyping (T, B, NK), CT of neck/chest/abdomen/pelvis
- Cycle 3&4 Day 5 (+/- 5 days): Research blood (up to 80ml, optional)
- Cycle 3&4 Day 14, and 22 (+/- 5 days): CBC with differential (may be performed outside of NIH), research blood (up to 80ml) (if the blood was drawn at the NIH)

Cycle 5

- Cycle 5 Day 1 (+/-5-day window): Lymphocyte phenotyping (T, B, NK)

Others

- Up to 3 lymph node biopsies may be obtained for research at any time during therapy (optional, with at least 4 weeks between biopsies).

After cycle 6 (+/- 14-day window):

Following assessments will be done every 3 months while on therapy until disease progression or intolerable side effects.

- Interval History
- ECOG performance status evaluation

- Physical exam
- Concomitant medication review
- CBC with differential
- Acute Care Panel (Na, K, Cl, CO₂, Creatinine, Glucose, and Urea Nitrogen)
- Mineral Panel (Phosphorus, Magnesium, Albumin, and Calcium)
- Total Protein, Uric Acid, and LDH
- Hepatic Panel (Alk Phosphatase, ALT, AST, Total Bilirubin, and Direct Bilirubin)
- Reticulocyte count
- Beta-2 microglobulin (B2M)
- Direct antiglobulin test (DAT)
- For females of childbearing potential, repeat pregnancy test
- Research blood (up to 80ml)

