9.0 BIOSTATISTICAL CONSIDERATIONS

9.1 Primary endpoint:

Primary efficacy endpoint is the rate of complete response at 24 weeks or after 6 cycles. Response to treatment will be determined according to IWCLL 2008 criteria incorporating 2012 and 2013 clarifications pertaining to patients treated with kinase inhibitors.

Primary safety endpoint is the rate of treatment discontinuation within the first 24 weeks or 6 cycles due to intolerable side effects.

9.2 Secondary endpoints:

- Progression-free survival (PFS)
- Overall survival (OS)
- Best response during treatment
- Duration of response
- Minimal residual disease (MRD) state defined by flow cytometry
- Clonal dynamics on treatment assessed using interphase FISH and gene sequencing for somatic mutations
- Shifts in cellular and humoral immunity on treatment (e.g. immunoglobulin levels, myeloid-derived stromal cells, B-cell repertoire, T-cell subsets including regulatory T cells, T helper 1, T helper 2, T helper 17)
- Expression of checkpoint inhibitory molecules such as PD-L1, PD-1, and CTLA-4

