9.7 Off Study Criteria (for subject participation)

Patient choice: Subjects may be removed from the study at their request. The risks of withdrawing will be discussed, as will alternative treatment options. Subjects who opt to withdraw from the protocol will be strongly encouraged to continue to have labs (CBC, chemistries) monitored for two months after study withdrawal for their safety.

PI Decision: Study drug administration will be discontinued for adverse events as detailed in section 5.5. These subjects will be followed until resolution of the event and continue to be followed on protocol. Other off study criteria include:

- Initiation of non-protocol treatment.
 - For patients who were newly diagnosed with a second malignancy, the study drug can be interrupted while the patient undergoes further evaluation and treatment with definitive, time-limited systemic therapy (i.e. breast cancer requiring surgery and adjuvant chemoradiation). If the new second malignancy requires long-term therapy (>6 months) or a definite therapy is not available (i.e. metastatic solid tumor), the patient will be taken off study.
- Significant progression of disease or a concomitant condition that would make the subject ineligible for further protocol participation. In selected cases, PI can decide if ibrutinib may be continued after progression until contingency plan for the next line of therapy is in place, and the benefit of treatment continuation outweighs potential risks.
- Pregnancy or begins breast feeding
- Subject becomes significantly noncompliant with study drug administration, study procedures, or study requirements, which might increase risk or substantially compromise the interpretation of study results.

Completion of the study: Subjects will be followed indefinitely until an off study criterion is met or the study is closed to further follow up care.

Once protocol participation is complete, the subject will be referred back to his or her referring physician, consented to the Hematology Branch evaluation and treatment protocol (94-H-0010) for consideration for standard therapy or evaluated for eligibility for another branch protocol, depending on what is considered to be in the best interest of the subject.

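### The section 5.2 therapy schedule ends ibrutinib at cycle 27, while the summary, 3.0 and 5.1 continue it until progression or intolerance

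*Combined protocol and SAP*

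**What the plan says.** Section 5.2 of the combined protocol and SAP is the operative dosing schedule. After the lines for cycles 1 and 2 and for cycles 3 and 4, its last bullet is "Cycle 5 and subsequent cycles up to C27: ibrutinib 420mg PO daily on day 1-28". Nothing follows for cycle 28 or later.

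Three other places state how long ibrutinib is given:

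- Protocol summary: "Ibrutinib will be given daily until disease progression or intolerable side effects occur".
- Section 3.0: "Ibrutinib will be given continuously until disease progression or intolerable side effects".
- Section 5.1, immediately before the schedule: "Ibrutinib will be given daily until disease progression or intolerable side effects".

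None of the three sets a maximum number of cycles.

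**The concern.** Two rules for treatment duration stand side by side, and they part company at the start of cycle 28. For a patient who is responding and tolerating ibrutinib at that point, 5.1 calls for the next dose and 5.2 schedules none.

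There are two things at stake. The first is treatment: read literally, the schedule takes an effective drug away from patients who are benefiting from it. The second is interpretation. The secondary endpoints in 9.2 include progression-free survival, duration of response and "Best response during treatment". Beyond about two years, these would describe a fixed course under one reading and continuous therapy under the other. If patients were handled differently, they would describe a mixture. There is also a compliance question, because which action at cycle 28 counts as a protocol deviation depends on which section is taken to govern.

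**Working it through.** **Inputs.** Cycle length is 28 days, plus or minus 5 (5.2). The last listed cycle is 27 (5.2). The primary endpoints are read at 24 weeks or 6 cycles (9.1). The stopping rule for treatment-related serious adverse events covers 6 months (9.5), and the mortality rule covers one year (9.6). Response is assessed after 6 cycles and then annually from first dose (6.3). The plan gives no calendar figure for the end of cycle 27, so there is none to reproduce.

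**Step 1: when the two rules diverge.**

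- Nominal end of cycle 27: 27 x 28 = 756 days; 756 / 30.44 = 24.8 months.
- First day of conflict: cycle 28 day 1 = 756 + 1 = day 757, counting the first dose as day 1.
- Outer bounds, with every cycle at the same extreme of the window: 27 x 23 = 621 days (20.4 months) and 27 x 33 = 891 days (29.3 months). These are limits and not a realistic range.

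**Step 2: what falls before that date.** Six cycles are 6 x 28 = 168 days, or 24 weeks. The 6-month and one-year stopping-rule periods also end well before even the 621-day bound. The primary efficacy and safety endpoints, both two-stage designs and both stopping rules therefore do not depend on the point.

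**Step 3: what falls after it.** On nominal timing the second annual response assessment is at about 2 x 365 = 730 days, before day 756. The third is at about 3 x 365 = 1,095 days, after it. Under a 27-cycle cap, the third and later annual assessments would be off drug and outside best response during treatment. Under continuous dosing they would be on drug.

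**Step 4: does other text reconcile the two?** The places that could do so are:

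| Place | What it says about duration |
|---|---|
| 5.5.3, permanent discontinuation | Lists adverse events, pregnancy or contraception, and "Progressive disease as defined in section 7.3"; no cycle number |
| 6.2, after cycle 6 | "Following assessments will be done every 3 months while on therapy until disease progression or intolerable side effects"; this schedules assessments, not dosing, but assumes open-ended therapy |
| 9.7, off-study criteria | Completing 27 cycles is not listed; in selected cases the "PI can decide if ibrutinib may be continued after progression until contingency plan for the next line of therapy is in place" |
| 12.1, dispensing | After cycle 6, supply to the next 3-monthly visit; no last cycle |
| 11.5, drug provision | Ibrutinib is supplied without charge; no time limit stated |
| Appendix A | Numbered cycles end at 5 and 6, then 3-monthly follow-up; cycle 27 does not appear |

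Cycle 27 is mentioned only in the 5.2 bullet. None of these places gives it a reason, such as a supply limit, a fixed treatment period or a change to commercial drug.

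**The case against.** The strongest reply is that 5.2 contains no order to stop. It lists a dose through cycle 27 and then falls silent, so a site that continues 420 mg under 5.1 at cycle 28 breaches no sentence of 5.2. On that view the bullet is incomplete and not contradictory. A site reading the whole protocol would probably continue treatment, and the effect on later endpoints stays hypothetical.

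Part of this stands. There is no explicit stop instruction, the weight of the text favours continuous dosing, and nothing shows that any site would stop. It does not remove the conflict. An explicit upper limit in the section that sets the therapy schedule is a dosing rule, and staff will look there for the dose.

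Some of the supporting context is also weak. The missing cycle 27 column in Appendix A proves little, because no cycle after the sixth has its own column. The argument rests on the three duration statements set against 5.2.

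Finally, the supply agreement is not reproduced and some pages are not available, so a deliberate cap cannot be excluded. If there is one, the three duration statements are wrong and the protocol still needs amending.

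**Conclusion.** The concern holds, as a minor error in the text. Section 5.2 limits scheduled ibrutinib to 27 cycles, three other statements set no limit, and no available text reconciles them. Section 5.2 is the likely outlier, although the documents do not say which section governs.

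The conflict begins at day 757 on nominal cycle lengths. It concerns only patients still on ibrutinib then, and it has consequences only if 5.2 is followed literally. How many patients that would be cannot be determined from the plan. As a rough indication, 2.6.2 cites 96% progression-free survival at 30 months with frontline ibrutinib. That figure comes from a different regimen and does not count stops for toxicity. The conclusions that depend on the first 6 cycles or the first year are untouched.

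**What to change.** In the last bullet of 5.2, replace the three words that set the cycle 27 limit with the duration rule already stated in 5.1: treatment until progression or intolerable side effects. The dose and days stay as they are.

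If a 27-cycle cap is really intended, state it and the reason for it in the summary, 3.0 and 5.1. Then align the discontinuation reasons in 5.5.3, the assessments in 6.2, the off-study criteria in 9.7 and the dispensing text in 12.1. The secondary endpoints should then be described as those of a fixed-duration regimen.

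The first option costs one short amendment, with no added subjects, visits or samples and no change to the sample size or decision rules.

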Drug	Cycle	Condition at the start of cycle	Action*
Ibrutinib	1 and onwards	ANC <500/μL OR PLT <50,000/μL	Check CBC with differential weekly. Hold ibrutinib if cytopenia persists for ≥ 7 days OR if PLT <50,000/μL with bleeding. Resume ibrutinib when ANC ≥750/μL AND PLT ≥50,000/μL. 
 • First occurrence: Resume ibrutinib at 420 mg once daily (original dose). • Second occurrence: Resume ibrutinib at 280 mg once daily. If cytopenia does not recur after 2 cycles of ibrutinib 280 mg once daily, investigator may increase ibrutinib to 420 mg once daily.
Fludarabine	3 and 4	HGB <11 g/dL with indications of autoimmune hemolysis	Omit fludarabine.
		ANC 750 - <1,000/μL OR PLT 50,000 - <75,000/μL	Defer fludarabine and check CBC with differential weekly. Resume fludarabine at original dose when ANC ≥1,000/μL AND PLT ≥75,000/μL. If count recovery does not occur in 8 weeks, omit fludarabine.
		ANC <500/μL, OR PLT <50,000/μL	Defer fludarabine, and check CBC with differential weekly. Resume fludarabine at 20% reduced dose when ANC ≥1,000/μL AND PLT ≥75,000/μL. If count recovery does not occur in 8 weeks, omit fludarabine.

ANC - absolute neutrophil count; PLT – platelet

* Dose delay or reduction is not required if cytopenia is considered related to CLL.

5.4.2 Atrial fibrillation:

- For new-onset atrial fibrillation, ibrutinib will be held until cardiac evaluation has been completed. The decision to restart ibrutinib will be made after the PI and consulting physician determine the subject is sufficiently stable following diagnostic testing and institution of treatment if required.
- Anticoagulation with atrial fibrillation: If anticoagulation is deemed necessary by consulting physician and/or PI, patients will be allowed to start treatment with anti-platelet or anti-coagulant therapies except warfarin. Co-administration with warfarin has been associated with grade 3 or higher bleeding events such as (subdural hematoma, gastrointestinal bleeding, hematuria, and post procedural hemorrhage). Other forms of anti-platelet, anti-coagulant, direct thrombin inhibitors, or factor Xa inhibitors may be used concomitantly with ibrutinib, however the risk of increased bruising or bleeding is unknown. Patients will be counseled and monitored closely for signs of bleeding and/or bruising and will be instructed to contact the research team and primary care physician in the case of any complications.

5.4.3 Non-hematologic toxicities:

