5.7 Permitted and Non Permitted Concomitant Medications (Investigators Brochure)

Patients may continue most medications they were prescribed prior to study enrollment for co-morbid conditions. No formal drug-drug interaction studies have been conducted therefore we ask patients to report all medications and over the counter drugs they are taking so we can monitor for any drug-drug interactions. Treatment for autoimmune cytopenias is permitted only during cycles with ibrutinib alone, but not during cycle 3 and 4 when fludarabine is added. Treatment for autoimmune cytopenias should not exceed 14 days at doses that do not exceed 100mg per day of prednisone or equivalent.

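### The fludarabine hold rules give no action for ANC 500-749, two restart doses for discordant counts, and conflicting instructions for autoimmune haemolysis

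*Combined protocol and SAP*

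**What the plan says.** Section 5.4.1 lists three fludarabine conditions, checked at the start of cycles 3 and 4.

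- Autoimmune haemolysis, "HGB <11 g/dL with indications of autoimmune hemolysis": the action is "Omit fludarabine", with no route back.
- Milder cytopenia, "ANC 750 - <1,000/μL OR PLT 50,000 - <75,000/μL": defer, check counts weekly, then "Resume fludarabine at original dose when ANC ≥1,000/μL AND PLT ≥75,000/μL".
- Severe cytopenia, ANC below 500/μL or platelets below 50,000/μL: defer, then "Resume fludarabine at 20% reduced dose when ANC" and platelets reach the same recovery thresholds.

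In both cytopenia rows fludarabine is omitted if counts have not recovered in 8 weeks. A footnote waives delay and reduction when the cytopenia is attributed to CLL. The ibrutinib row acts at "ANC <500/μL OR PLT <50,000/μL".

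Section 5.5.2 covers medical reasons for holding: "If medically necessary reasons to hold fludarabine occur during treatment (i.e. concurrent infection, emergence of autoimmune cytopenia" and diagnostic or therapeutic workups. In these cases fludarabine may be delayed for up to two cycles while ibrutinib continues, and is omitted after that.

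**The concern.** A hold table for a cytotoxic drug should give one action for every count below the treatment threshold. This one defers a patient with ANC 800 and a patient with ANC 400 but is silent on a patient with ANC 600 and adequate platelets. The stated rule therefore protects a more neutropenic patient less than a milder one. Some discordant counts lead to two restart doses. One autoimmune state leads either to no fludarabine for that course or to a later course.

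The gap is reachable. Section 4.1 admits patients with ANC just above 750/μL, section 2.7 puts neutropenia first among Grade 3 or 4 events both for ibrutinib alone and in combinations, and cycle 4 follows a fludarabine course. The grading scale in section 10.1.1 makes ANC 500 to <1,000/μL Grade 3. Section 10.0 says that these two drugs have not been combined in a trial before. At stake are dosing safety and a regimen that can be described in one way.

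**Working it through.** **Step 1: apply the cytopenia rows to pairs of counts.** Inputs are the cut-points in section 5.4.1. The rows were applied to ANC 300 to 1,200 in steps of 50 (19 values) at platelets of 40,000, 60,000 and 80,000, which gives 19 × 3 = 57 pairs. A pair is clear for treatment only if ANC ≥1,000 and platelets ≥75,000.

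| Counts (per μL) | Milder row | Severe row | Result |
|---|---|---|---|
| ANC 800, PLT 80,000 | yes | no | defer, original dose |
| ANC 600, PLT 80,000 | no | no | no action stated |
| ANC 400, PLT 80,000 | no | yes | defer, 20% less |
| ANC 600, PLT 60,000 | yes (platelets) | no | defer, original dose |
| ANC 900, PLT 40,000 | yes (ANC) | yes (platelets) | defer, two restart doses |
| ANC 400, PLT 60,000 | yes (platelets) | yes (ANC) | defer, two restart doses |

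Five pairs meet no row: ANC 500, 550, 600, 650 and 700, all at platelets 80,000. Nine pairs meet both rows: ANC 300-450 at platelets 60,000 (four) and ANC 750-950 at platelets 40,000 (five). These are counts of grid points, not expected frequencies. The platelet bands in the same cells are contiguous (50,000 to <75,000, then <50,000), so the break in the ANC bands looks like a drafting slip.

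**Step 2: size of the dose difference.** Section 5.1 gives 25 mg/m²/day for 5 days, or 25 × 5 = 125 mg/m² per course. Twenty percent less is 20 × 5 = 100 mg/m². Discordant counts leave a 25 mg/m² difference per course open. For the gap, the deferral and the restart dose are both unstated.

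**Step 3: the haemolysis rules side by side.** A patient with haemoglobin 10 g/dL and signs of autoimmune haemolysis at the start of cycle 3 meets the first row of 5.4.1 (omit). That patient also has an emerging autoimmune cytopenia under 5.5.2 (may delay up to two cycles, give if resolved, otherwise omit). Neither section says which prevails.

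**Step 4: check that the design figures are untouched.** Section 9.3 stops for efficacy at 0 CRs in 13 and rejects the null at 4 or more in 27. The rejection probability is Σ over x = 1 to 13 of b(x; 13, p) × P(Y ≥ 4 − x), with Y ~ Bin(14, p). It is 0.801 at p = 0.20 and 0.042 at p = 0.05, which matches the stated 80% power and 0.05 limit. The safety rule (continue at 2 or fewer of 13, reject at 4 or fewer of 27) gives 0.809 at 10% and 0.047 at 30%, which matches the stated 81% and 0.05.

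**The case against.** The best defence is that a sensible clinician would not be misled. Silence at ANC 500-749 is not an instruction to treat: every resume rule needs ANC ≥1,000, and 5.5.2 lets the team hold for medical reasons. Neither the ANC cut-points nor the platelet cut-points overlap by themselves. Where two rows apply they agree on deferral, recovery threshold and the 8-week limit, and taking the worse row settles the dose. On haemolysis, 5.4.1 can be read as the specific rule and 5.5.2 as the general, permissive one for other autoimmune cytopenias. The footnote also removes CLL-related cytopenia from mandatory deferral.

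Much of this stands, and it limits the harm. But the protocol states none of these resolutions, and the restart dose in the ANC gap cannot be inferred.

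A reader might infer more than the text supports:

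- *That section 5.7 is also in conflict.* It says "Treatment for autoimmune cytopenias is permitted only during cycles with ibrutinib alone, but not during cycle 3 and 4 when fludarabine is added". A cycle in which fludarabine is delayed is an ibrutinib-alone cycle, so treatment is allowed then, and 5.5.2 and 5.7 fit together.
- *That practice would differ between sites.* Section 3.0 describes a single-center trial.
- *That the 37% figure for autoimmune haemolytic anaemia in section 2.2 measures the problem.* It is a background disease figure, and section 4.2 excludes active autoimmune haemolytic anaemia or thrombocytopenia at entry.

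**Conclusion.** Three faults stand: no action for ANC 500-749 with platelets ≥75,000, an unsettled restart dose for discordant counts, and an unreconciled instruction for haemolysis with haemoglobin below 11 g/dL. They are errors in operative dosing rules and should be corrected, mainly for dosing safety in a first-use combination.

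It is tempting to conclude that the primary results are compromised because regimens are mixed. The documents do not show this. Any rule with full, reduced and omitted branches mixes regimens, including a corrected one, and no endpoint, sample size or decision rule changes. The documents give no figure for how many patients would meet these conditions.

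Purely for scale, assume that a fraction f omits fludarabine and has a CR rate q, so that p = 0.20(1 − f) + qf. With f = 10%, q = 5% gives p = 0.185 and power 0.745; q = 13% (the ibrutinib-alone rate cited in section 9.3) gives p = 0.193 and power 0.776, against 0.801 at f = 0. The value of f is an assumption. The ANC gap and the discordant-count problem do not themselves cause omission; only the haemolysis conflict bears directly on it. These figures are not an estimate of harm.

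**What to change.** 1. Make the ANC bands contiguous. The conservative choice is to change the last fludarabine row to ANC <750/μL OR PLT <50,000/μL, with restart at 20% less. If the investigator prefers an original-dose restart, extend the middle row to ANC 500 to <1,000/μL instead.
2. Add one line: when counts meet two rows, the more severe row governs.
3. State in 5.5.2 that autoimmune haemolysis with haemoglobin below 11 g/dL at the start of cycle 3 or 4 follows 5.4.1 (omit), and that the delay option applies to other autoimmune cytopenias.

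With items 1 and 2, every pair of counts below ANC 1,000 or platelets 75,000 has exactly one action. The choice of restart dose is clinical and belongs to the investigator. The cost is a short amendment to 5.4.1 and 5.5.2, with no added patients or procedures.
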